8 STATISTICAL CONSIDERATIONS

8.1 Study Populations

Efficacy population — all enrolled subjects who received at least one dose of the study drug and have either died or have at least one evaluation of PSA after the initiation of study treatment.

Safety population — all enrolled subjects who received at least one dose of the study drug.

8.2 Study hypotheses

The null hypothesis that the median PSA-progression-free survival is six months will be tested against a one-sided alternative by for the six-month PSA-progression-free survival probability exceeding 50%. The study is designed to have 80% power to obtain a result significant at a one-sided 10% level if the experimental treatment has a six-month PSA-progression-free probability of 66%, which corresponds to a median of 10 months if the time to PSA progression is exponentially distributed.(84)

8.3 Study design and sample size

A two-stage single-arm design based on the methods of Huang et al (2010) will be used.

The design is based on a modification of a binomial two-stage design that allows the incorporation of data from subjects with less than six months of follow-up at the interim analysis. The study will enroll up to 46 subjects with an interim analysis performed when 10 patients have been treated and followed for 6 months. The underlying binomial design would stop for futility if there are four or fewer patients alive without PSA progression at six months among these 10 patients. The modified futility decision will use the Kaplan-Meier estimate of the six-month PSA-progression-free survival using the data from the first 10 subjects and any subject who have been enrolled during the six-month follow-up period of the tenth subject. If the six-month PSA-progression-free survival is significantly lower at a one-sided 10% significance level than the clinically meaningful value of 66% defined by the alternative hypothesis, the study will be stopped for futility. If no new patients would be enrolled during the follow-up period, this decision rule is equivalent to the one defined by the binomial design.

If the study is not stopped for futility, study enrollment continues until 46 subjects are enrolled. The final analysis will be performed when all subjects have been followed for at least six months. The null hypothesis will be rejected, and the study drug will be considered promising if 27 or more patients are alive without PSA progression at six months among the 46 patients. The underlying binomial design yields a type I error rate of 10% if the underlying six-month PSA-progression-free probability is 50% (and the median PSA-progression-free survival is 6 months), and power of 80% when the six-month PSA-progression-free probability is 66%, which corresponds to a median of 10 months if the time to PSA progression is exponentially distributed. Simulation studies confirmed that the design with the modified futility stopping method maintains these properties. If the median PSA-progression-free survival is six months, then the binomial design would stop at the interim analysis with 38% probability. Assuming an enrollment rate of 1.5 subjects/month, the modified futility stopping rule increases this probability of stopping at the interim analysis to 45%.

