8.4 Analysis of primary endpoint

The probability of PSA-progression-free survival over time will be estimated using the Kaplan-Meier method and shown with 80% pointwise confidence limits. The six-month PSA-progression-free survival will be compared to the null-value of 50% using a z-test at a one-sided 10% significance level.

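### The final rule of 27 or more out of 46 has a type I error of 13.3%, not 10%, and the Section 8.4 z-test, read untransformed, does not reject at 27

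*Combined protocol and SAP*

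**What the plan says.** Section 8.2 and the Statistics row of the protocol summary set the targets: "The study is designed to have 80% power to obtain a result significant at a one-sided 10% level" when the six-month PSA-progression-free probability is 66%, against a null value of 50%.

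Section 8.3 gives the design. An interim look at 10 patients stops for futility at four or fewer successes; otherwise enrollment runs to 46. At the end, "The null hypothesis will be rejected, and the study drug will be considered promising if 27 or more patients are alive without PSA progression" (judged at six months). On error rates it says "The underlying binomial design yields a type I error rate of 10% if the underlying six-month PSA-progression-free probability is 50" percent, and claims "power of 80% when the six-month PSA-progression-free probability is 66" percent. It adds that simulation confirmed these properties under the modified, Kaplan-Meier-based futility rule. It puts the null stopping probability at 38% for the binomial rule and 45% for the modified rule at 1.5 subjects per month.

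Section 8.4, the analysis of the primary endpoint, gives a different final test. The Kaplan-Meier six-month estimate "will be compared to the null-value of 50% using a z-test at a one-sided 10% significance level". No variance formula or transformation is named. Section 8.10 censors patients whose primary outcome is missing.

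**The concern.** There are two linked problems. First, the error rates in Section 8.3 do not belong to the rule printed beside them: 27 of 46 is too low a bar for a 10% test against 50%. Second, Sections 8.3 and 8.4 each state a final test of the same null hypothesis, and the two do not share a rejection region.

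This is the trial's only formal efficacy decision. If exactly 27 patients succeed, one section calls the drug promising and the other calls the result non-significant, so the choice between them would be made after the data are seen. If the count governs, the type I error is about a third above its stated value (13.3/10 = 1.33). If the z-test governs, power is below the stated 80%.

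**Working it through.** **Inputs.** From Section 8.3: n1 = 10, stop if x1 ≤ 4, N = 46 (36 patients in stage 2), reject if the total is c = 27 or more, p0 = 0.50, p1 = 0.66. From Sections 8.2 and 8.4: one-sided 10%, critical value 1.2816.

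**1. The plan's own stopping figure.** P(X1 ≤ 4 | n = 10, p = 0.5) = 386/1024 = 0.377. This matches the stated 38%, so the design has been read correctly.

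**2. Exact rejection probability.** P(reject) = Σ over x = 5 to 10 of P(X1 = x) × P(Bin(36, p) ≥ c − x). For c = 27:

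| x | p = 0.50 | p = 0.66 |
|---|---|---|
| 5 | 0.2461 × 0.1215 = 0.0299 | 0.1434 × 0.7886 = 0.1131 |
| 6 | 0.2051 × 0.2025 = 0.0415 | 0.2320 × 0.8734 = 0.2026 |
| 7 | 0.1172 × 0.3089 = 0.0362 | 0.2573 × 0.9307 = 0.2395 |
| 8 | 0.0439 × 0.4340 = 0.0191 | 0.1873 × 0.9655 = 0.1808 |
| 9 | 0.0098 × 0.5660 = 0.0055 | 0.0808 × 0.9844 = 0.0795 |
| 10 | 0.0010 × 0.6911 = 0.0007 | 0.0157 × 0.9936 = 0.0156 |
| Sum | **0.1329** | **0.8311** |

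The same sum for c = 28 gives **0.0833** and **0.7724**. The rejection probability falls as c rises, so no cut-off at N = 46 with this interim rule gives type I error ≤ 10% and power ≥ 80% together.

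**3. Could another reading give 10% and 80%?** With c = 27:
- No futility stop: type I error 15.1%.
- Stopping at 3 or fewer of 10: 14.7%.
- Stopping at 5 or fewer of 10: 10.3%, but power is only 71.8%.
- Modified Kaplan-Meier interim, simulated with exponential times and 1.5 subjects per month (20,000 runs): null stopping 0.452, matching the stated 45%; type I error about 0.13 and power about 0.83.

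The modified rule therefore reproduces the plan's stopping figure but not its error rates.

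**4. The Section 8.4 test at 27 of 46.** With no one censored before six months, the Kaplan-Meier estimate is 27/46 = 0.587.
- Greenwood SE = √(0.587 × 0.413/46) = 0.0726; z = 0.0870/0.0726 = 1.198; p = 0.115.
- Null SE = √(0.25/46) = 0.0737; z = 0.0870/0.0737 = 1.180; p = 0.119.

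Both are below 1.2816. The lower limit of the 80% interval that Section 8.4 will display is 0.587 − 1.2816 × 0.0726 = 0.494, below the null value. At 28/46 = 0.609, z is 1.511 (Greenwood) or 1.474 (null SE), and both reject. So with complete data the untransformed z-test is the rule of 28 or more. Simulated with the modified interim, it has type I error about 0.08 and power about 0.77.

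**5. Loss before six months (illustration only).** The documents give no loss rate. Read literally, the count needs 27 successes among all 46, so a lost patient cannot count, whereas Section 8.10 censors him. Multiplying each success probability by (1 − loss) in the step 2 sum gives, for the count rule:

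| Assumed loss | Type I error | Power |
|---|---|---|
| 5% | 0.074 | 0.71 |
| 10% | 0.038 | 0.55 |
| 15% | 0.017 | 0.38 |

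A simulation at 10% loss gives about 0.04 and 0.58 for the count, against about 0.09 and 0.77 for the z-test. With losses, the two rules can disagree in either direction.

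**The case against.** The strongest reply concerns the conflict between the rules, not the arithmetic. Section 8.4 names no scale. A z-test on the log-survival scale gives 1.296 at 27 of 46 and would just reject. That is true, but a log-scale interim test stops about 35% of the time under the null, whereas the untransformed scale reproduces the stated 45%, so untransformed is the likelier intention. The null-variance, continuity-corrected, arcsine and log(−log) versions also fail to reject. If the log scale was meant, with complete data the test would agree with the count at 27 and share its 13.3%.

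It can also be said that Section 8.4 plainly governs, since it is headed as the primary analysis and Section 8.10 supports censoring. Type I error would then be about 8%, and the harm only about three points of power. That is a fair reading, but Section 8.3 states its rejection rule without qualification and nothing ranks the two.

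The overlap is narrow: with complete data the rules differ only at exactly 27 successes, about 5% of trials under the null (13.3 − 8.3) and 6% under the alternative (83.1 − 77.2). This limits the practical reach but does not correct the stated error rates. The loss figures rest on assumed rates and on counting lost patients as failures, so they are a side illustration.

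**Conclusion.** The concern holds. The rule in Section 8.3 has an exact type I error of 13.3% and power of 83.1%, against the stated 10% and 80%. This rests only on figures printed in that section and is not altered by the modified futility rule. The Section 8.4 test, taken untransformed and with no censoring before six months, is equivalent to 28 or more of 46, with 8.3% and 77.2% under the binomial interim rule. Neither rule delivers the promised 10% and 80%, and the two give opposite conclusions at 27 of 46. The conflict at 27 depends on the untransformed scale; the misstated error rates do not. This must be corrected before the final analysis.

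**What to change.** Keep one primary decision rule and state its true operating characteristics in the protocol summary and Sections 8.2 to 8.4.

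- **Preferred:** make the Section 8.4 Kaplan-Meier z-test primary and specify the untransformed scale and the variance estimator. In Section 8.3, change the count to 28 or more, described as equivalent only when no one is censored before six months. State about 8% type I error and 77% power.
- **Alternative:** keep 27 or more as the rule, state 13.3% and 83%, delete the 10% z-test, and say how patients lost before six months are counted.

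Either way, correct the sentence saying that simulation confirmed the 10% and 80%. The cost is wording, plus accepting a lower stated power or a higher stated type I error. No patients or visits are added.

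The trial statistician should first recheck where the cut-off came from. A rule of 27 of 45 with the same interim gives 10.4% and 79.7%, which round to the stated figures, but the protocol says 46 throughout, so that origin is conjecture. If 10% and 80% must both be met exactly, N has to change: the step 2 formula with N = 50 and c = 30 gives 9.0% and 80.3%, at a cost of four more patients.

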PAC203 Phase 2 Safety Observations

The most common treatment-emergent non-hematologic AEs were GI, including diarrhea (23.6%) and nausea (23.6%), and were distributed similarly across treatment arms. The most common hematologic AEs were thrombocytopenia and anemia, both occurring at higher frequencies in the

200 mg pacritinib BID group (35.2% and 24.1%, respectively); this did not, however, lead to higher rates of grade 3 /4 hemorrhage at higher doses (200 mg pacritinib BID: 5.6%; 100 mg pacritinib BID: none; and 100 mg pacritinib QD: 7.7%). A slightly higher percentage of patients in the 200 mg pacritinib BID group had grade 3 or 4 TEAEs (74.1%) compared with the other treatment groups, possibly due to higher rates of thrombocytopenia and anemia at baseline in the 200 mg pacritinib BID group compared with the other treatment groups. Across the treatment groups, no notable shifts from Baseline to a higher worst post-baseline grade were observed for hemoglobin, platelets, leukocytes, neutrophils, lymphocytes, or partial thromboplastin time (PTT). The incidence of clinically significant laboratory abnormalities was low across the treatment groups.

Overall, 19.3% of patients had a TEAE leading to study drug interruption, and the incidence was higher in the 200 mg pacritinib BID group compared with the other treatment groups. The most common TEAE leading to study drug interruption was thrombocytopenia (3.7%). The most common type of TEAE leading to study drug interruption was in the system organ class of infections and infestations (5.6% overall); the incidence was higher in the 200-mg pacritinib BID group (11.1%) compared with the other treatment groups (100-mg pacritinib BID group: 5.5%; 100 mg pacritinib QD group: none). One of the infections was an opportunistic infection (herpes esophagitis in the 200 mg pacritinib BID group). Altogether, 17.4% of patients had a TEAE leading to study drug discontinuation, and the incidence was higher in the 100 mg pacritinib BID group compared with the other treatment groups. The most common TEAE leading to study drug discontinuation was thrombocytopenia (3.7% overall).

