4.6 Discontinuation of Study Treatment, Withdrawal, and Compliance

Treatment duration is 2 years. Patients may continue drug beyond two years if, in the opinion of the treating physician, the patient is benefitting from treatment and benefits outweigh any risks of therapy

Discontinuation from the study treatment does not mean discontinuation from the study. The subject will be considered in follow-up, study procedures should still be completed as indicated by the study protocol, and AEs/SAEs will continue to be reported according to this protocol.

In the absence of treatment delays due to adverse events, study treatment/intervention may continue until:

- Disease progression per PCWG3 guidelines
- General or specific changes in the subject's condition renders the subject unacceptable for further treatment in the investigator's judgment.
- An inter-current illness that prevents further treatment administration.
- The subject decides to withdraw from the study.
- The subject has significant noncompliance with the protocol (see below).
- Unacceptable adverse event(s) and/or dose level reduction beyond requirements as detailed in this protocol.
- The clinical need for concomitant therapy that is not permitted in the study.
- Subjects who sign the informed consent form, enroll and receive the study intervention, but subsequently withdraw, or are withdrawn or discontinued from the study will not be replaced.

Progression of disease

Progression of disease per PCWG3 is defined as one or more of the following:

PSA progression

Recognize that a favorable effect on PSA may be delayed for \geq 12 weeks, even for a cytotoxic drug. Monitor PSA by cycle but plan to continue through early rises for a minimum of 12 weeks unless other evidence of progression.

If there is a decline in PSA from baseline: record time from baseline to the first PSA increase that is $\geq 25\%$ and ≥ 2 ng/mL above the nadir, and which is confirmed by a second value ≥ 3 weeks later (i.e., a confirmed rising trend).

If there is no decline in PSA from baseline but stable PSA at 12 weeks: PSA progression will be defined as $\geq 25\%$ and ≥ 2 ng/mL from PSA at 12 weeks .

Radiographic progression

Radiographic progression will be assessed per RECIST 1.1. Any new unequivocal bone lesion is considered progression, except if that lesion appears in the first post-treatment scan; in that

case, document the event, continue treatment until two additional new lesions appear, and record both events.

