8.9 Interim analyses

An interim analysis for futility will be performed when 10 patients have been treated and followed for six months. The Kaplan-Meier estimate of the six-month PSA-progression-free survival using the data from the first 10 subjects and any subject who have been enrolled during the six-month follow-up period of the tenth subject will be computed and compared to 66% using a z-test at a one-sided 10% significance level. The study will be stopped for futility if the hypothesis is rejected for the alternative of the 6-month PSA-progression-free survival being lower than 66%.

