8.10 Missing data

For all outcomes, summary statistics will include the count of missing and non-missing values. Patients with missing value for the primary outcome, PFS, will be censored at the time when last known to be alive and without progression. A similar approach will be used for other time-to-event outcomes, such as time to PSA nadir. Secondary outcomes requiring numeric values, such as geriatric assessments, PSA and testosterone levels will be analyzed among patients with non-missing values as required for each analysis (e.g., non-missing value at specific time point for cross-sectional analysis, and non-missing values at two time points for change analyses). The limitations of extensive missingness, if present, will be clearly noted in all reports and any related findings will be interpreted with caution.

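### Sections 8.3 and 8.4/8.10 give two final decision rules that can disagree, and only the second can handle a man whose six-month PSA status is unknown

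*Combined protocol and SAP*

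**What the plan says.** - **Final rule in 8.3.** If the trial passes the interim, "study enrollment continues until 46 subjects are enrolled", and the null is rejected if "27 or more patients are alive without PSA progression at six months among the 46 patients". Section 8.3 credits the underlying binomial design with 10% type I error at a 50% rate and 80% power at 66%. The final analysis waits until everyone has been followed for at least six months.
- **Primary analysis in 8.4.** The six-month Kaplan-Meier estimate is compared with 50% by a z-test at a one-sided 10% level.
- **Missing outcomes in 8.10.** Men with no primary outcome "will be censored at the time when last known to be alive and without progression".
- **Withdrawals in 4.6.** Treated men who leave, "but subsequently withdraw, or are withdrawn or discontinued from the study will not be replaced". No dropout allowance appears in 8.3.
- **Interim rule in 8.3 and 8.9.** The binomial version "would stop for futility if there are four or fewer patients alive without PSA progression at six months among these 10 patients". The version to be used takes a Kaplan-Meier estimate that "will be computed and compared to 66% using a z-test at a one-sided 10% significance level".

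No section says whether the 8.3 count or the 8.4 z-test settles the result, or how a man with unknown six-month status enters the count.

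**The concern.** A man censored at month 3 is not known to be progression-free at month 6. He cannot add to the 27, and neither the threshold nor the 46 adjusts for him. If 8.3 decides, he is in effect scored as a failure. If 8.4 and 8.10 decide, he contributes the time for which he was observed. The same data can therefore be a success under one section and a failure under the other. Unless the choice is fixed beforehand, it could be made after the data are seen.

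**Working it through.** **1. The plan's own figures.** Inputs from 8.3: 10 men in stage 1, continue if at least 5 are event-free; 46 in total, success at 27; rates 50% and 66%.

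- Early stopping under the null: P[Bin(10, 0.5) ≤ 4] = 37.7% (stated 38%). Simulating the Kaplan-Meier interim rule at 1.5 men a month with exponential times gives 45.4% (stated 45%). Both reproduce.
- Chance of declaring success: sum over x = 5 to 10 of P[Bin(10, p) = x] × P[Bin(36, p) ≥ 27 − x]. At p = 0.50 this is 13.3% (stated 10%); at p = 0.66 it is 83.1% (stated 80%). These do not reproduce. A threshold of 28 gives 8.3% and 77.2%.

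**2. The count rule with unknown statuses.** Let k stage 2 men have no six-month status, unrelated to outcome. None can add to the 27, so 36 becomes 36 − k in the second term.

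| k | Type I error (p = 0.50) | Power (p = 0.66) |
|---|---|---|
| 0 | 13.3% | 83.1% |
| 1 | 10.4% | 79.7% |
| 2 | 8.0% | 75.4% |
| 3 | 5.9% | 70.1% |
| 5 | 2.8% | 56.4% |

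Two men are 2/46 = 4.3% of the sample. With the Kaplan-Meier interim rule and two losses at random, simulation gives 75.5% power and 8.0% type I error, so the result does not depend on placing the losses in stage 2.

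**3. The 8.4 z-test on the same trial.** Simulated with the Kaplan-Meier interim rule, 1.5 men a month, exponential event times and censoring independent of outcome. Plain Greenwood standard error unless stated.

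| Loss before six months (assumed) | Type I error | Power |
|---|---|---|
| None | 8.2% | 77.6% |
| 2 men | 9.7% | 78.8% |
| 5 men | 9.5% | 77.4% |
| 5%, 10%, 17.4% of men | 9-10% | 78%, 77%, 77% |

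The plan does not specify the variance. A log-log version gives about two points less power: 76.5% with two men censored and 75.6% with five, at 8.4% and 8.3% type I error.

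**4. Where the rules disagree.** The one-sided 10% critical value is 1.28. With complete data the Kaplan-Meier estimate is the simple proportion s/n, and z = (s/n − 0.5) / √[(s/n)(1 − s/n)/n].

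- 27 of 46, nobody lost: 0.5870 − 0.5 = 0.0870; SE = 0.0726; z = 1.20. The count succeeds and the z-test fails.
- 28 of 46, nobody lost: 0.1087 / 0.0720 = 1.51. Both succeed.
- Three men censored before any event, 26 of the other 43 event-free: 0.1047 / 0.0746 = 1.40. The count fails (26 < 27) and the z-test succeeds.

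**5. The interim, for contrast.** Against 66%, 4 of 10 gives z = (0.40 − 0.66)/0.1549 = −1.68 (stop) and 5 of 10 gives (0.50 − 0.66)/0.1581 = −1.01 (continue). The count and z-test agree at the interim when nobody new has enrolled, as 8.3 says. No such agreement holds at the final analysis.

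**The case against.** The strongest reply is that the plan already handles missing outcomes. Section 8.4 is the stated analysis of the primary endpoint, 8.10 censors, and under those sections a lost man is not a failure. That is right, and the z-test figures bear it out. A reader might infer that censoring itself counts against the drug; it does not. The penalty arises only if the 8.3 count decides. But 8.3 is where the plan says when the null is rejected, and nothing subordinates it to 8.4.

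Second, the size should not be exaggerated. The count rule starts from 83.1% power because its type I error is 13.3%. With one unknown status it sits almost exactly at the stated 10% and 80%. With two, its 75.4% power comes with 8.0% type I error, against about 77-79% at 8-10% for the z-test. The two tests differ in size, so part of the power gap is a gap in type I error. This stands.

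Third, scoring unknown statuses as failures is a recognised conservative choice when withdrawal may be informative. That also stands, but the plan does not state the choice, and 8.10 says something else.

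Two further inferences are tempting and unsupported:

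- **A loss rate near 17%.** The PAC203 summary in 1.5.4 reports that "17.4% of patients had a TEAE leading to study drug discontinuation". That is stopping drug for adverse events, across three dose arms, in myelofibrosis patients. Section 4.6 says that stopping treatment is not leaving the study and keeps such men in follow-up. It is not an expected loss rate here.
- **An expectation of dropout behind the interim rule.** The Kaplan-Meier interim rule exists to use men enrolled while the tenth man is being followed. That is staggered entry. It does not show that the authors expected dropout and overlooked it at the end.

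**Conclusion.** The point holds as a conflict between two final decision rules. The count needs all 46 statuses, in a plan with no replacement and no loss allowance; if it decides, each unknown status lowers power, to 75.4% with two. The 8.4 z-test is almost unaffected by non-informative censoring. The two rules give opposite results at 27 of 46 even with nobody lost. Neither rule has the stated 10% and 80% with complete data: the count gives 13.3% and 83.1%, the z-test about 8% and 77%.

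The exact count-rule figures assume that unknown status is unrelated to outcome. The z-test figures also assume exponential times and accrual of 1.5 men a month. All loss levels are assumptions. The documents do not support the stronger claim that the trial will lose a large share of its power, because they give no loss rate and do not say that the count overrides the Kaplan-Meier analysis.

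**What to change.** - In 8.3 and in the Statistics row of the protocol summary, name the 8.4 Kaplan-Meier z-test (six-month estimate against 50%, one-sided 10%) as the only final success criterion, and state the variance formula.
- Remove the 27-of-46 rule, or replace it with 28 of 46, described as the equivalent when no man is censored before six months. Keeping 27 as that equivalent would be false.
- Restate power as about 77% and type I error as about 8-10%, with the loss assumption and the simulation settings given.
- Report alongside it a sensitivity analysis that counts unknown six-month statuses as failures.

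This costs wording and a short simulation, with no extra patients or visits. The price is a stated power below 80% at 46 men and reliance on non-informative censoring, which 8.4 and 8.10 already assume. The sensitivity analysis shows how far the conclusion depends on that assumption.
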